5.2.1 Treatment interruption and treatment discontinuation

All dose modifications should be based on the worst preceding toxicity. Generally, all dose interruptions or treatment discontinuation will be based on investigational drug-related AEs. For

reasons other than drug-related AEs, eg, safety concerns due to the poor health condition, if deemed necessary by the investigators, dose modifications could be applied after discussion with medical monitor.

Each patient is only allowed up to 2 dose reductions. In addition, a patient must discontinue treatment with pamiparib if, after treatment is resumed at a lower dose, the toxicity recurs with the same or worse severity.

Toxicity		Recommended Dose Modification ^a			
Hematologic					
Anemia (hemoglobin, Hgb)					
Hgb < 9.0 g/dL		 First occurrence of Hgb < 9.0 g/dL: Hold pamiparib and treat as medically indicated to get Hgb to ≥ 9 g/dL, and then ↓ pamiparib by 1 dose level to 40 mg BID 			
Grade 2 (8 ≤ Hgb <10	$9 \le Hgb < 10$ g/dL	• Continue dosing at current dose level and treat with appropriate supportive care as medically indicated			
g/dL)	$8 \le Hgb < 9 g/dL$	 Subsequent occurrence following dose reduction for anemia: Continue pamiparib without interruption with appropriate supportive care based on clinical assessment OR Hold pamiparib and treat as medically indicated to get Hgb to ≥ 9 g/dL, then restart at reduced dose level OR Hold pamiparib and treat as medically indicated to get Hgb to ≥ 9 g/dL, then √ pamiparib by 1 additional dose level to 20 mg BID 			
Grade 3 (Hgb < 8 g/dL)		 Subsequent occurrence following dose reduction for anemia: Continue pamiparib without interruption with appropriate supportive care based on clinical assessment OR Hold pamiparib and treat as medically indicated to get Hgb to ≥ 9 g/dL, then restart at reduced dose level OR Hold pamiparib and treat as medically indicated to get Hgb to ≥ 9 g/dL, then √ pamiparib by 1 additional dose level to 20 mg 			

BID

Table 9.	Criteria for interruption and re-initiation of Pamiparib due to treatment
associated ad	verse event

Toxicity	Recommended Dose Modification ^a

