Grade 4 (life-threatening consequences; urgent intervention indicated)	 Second occurrence following dose reduction for anemia: Hold pamiparib and treat as medically indicated to get Hgb to ≥ 9 g/dL, then ↓ pamiparib by 1 additional dose level to 20 mg BID Third occurrence following 2 dose reductions for anemia: Discontinue pamiparib if anemia is not caused by any other confounding event, eg GI hemorrhage. Hold pamiparib and treat as medically indicated to get Hgb to ≥ 9 g/dL, then restart at reduced dose level.
 higher anemia, hematolog 2) For any patients showing explanation such as gastro 3) Dose increase can be considered 	should be done for the first 3 cycles during the study. For all Grade 2 or gy test should be done weekly thereafter until adequate recovery. Hgb dropping > 2 g/dL especially within a short time without alternative pointestinal bleeding, ψ pamiparib by 1 dose level should be considered sidered in certain cases, depending on approval from the medical monitor, naintained above 9 g/dL for at least 3 months
Neutropenia (absolute neutroph	il count, ANC)
Grade 3 (ANC <1.0 - 0.5 × 10 ⁹ /L)	 Hold pamiparib until resolved to Grade ≤2 or baseline If resolved ≤7 days, then maintain dose levels If resolved >7 days, then ↓ pamiparib by 1 dose level
Grade 4 (ANC $< 0.5 \times 10^{9}/L$)	Hold pamiparib until resolved to Grade ≤ 1 or baseline and ψ pamiparib by 1 dose level
Febrile neutropenia (ANC $<1.0 \times 10^{9}$ /L with single temperature of >38.3°C or sustained temperature of \geq 38°C for >1 hour)	Hold pamiparib until resolved and ↓ pamiparib by 1 dose level
Thrombocytopenia (platelet cou	unt, PLT)
Grade 3 (PLT <50 - 25 × 10 ⁹ /L)	 Hold pamiparib until resolved to Grade ≤1 or baseline If resolved ≤7 days, then maintain dose levels If resolved >7 days, then ↓ pamiparib by 1 dose level
Grade 4 (PLT $<25 \times 10^{9}/L$)	Hold pamiparib until resolved to Grade ≤1 or baseline and ↓ pamiparib by 1 dose level

Toxicity	Recommended Dose Modification ^a			
Renal				
Estimated glomerular filtration rate (CKD-EPI EQ; Appendix 6)				
If $\geq 60 \text{ mL/min}/1.73 \text{ m}^2$ at baseline: <30 to 15 mL/min/1.73 m ² or If <60 mL/min/1.73 m ² at baseline: $\geq 50\%$ reduction from baseline	 Hold pamiparib until resolved to ≥60 mL/min/1.73 m² If resolved ≤7 days, then maintain dose levels If resolved >7 days, then ↓ pamiparib by 1 dose level 			
Regardless of baseline: <15 mL/min/1.73 m ²	Permanently discontinue pamiparib			
Hepatic				
Bilirubin				

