Grade 2 (>1.5 - 3.0 × ULN) Only applies to patients with normal bilirubin at baseline	 Hold pamiparib until resolved to Grade ≤1 or baseline If resolved ≤7 days, then maintain dose levels If resolved >7 days, then ↓ pamiparib by 1 dose level 			
Grade 3 (>3.0 - 10.0 × ULN)	 Hold pamiparib until resolved to Grade ≤1 or baseline If resolved ≤7 days, then maintain dose levels If resolved >7 days, then ↓ pamiparib by 1 dose level 			
Grade 4 (>10.0 × ULN)	Permanently discontinue pamiparib Note: If Grade 3 or 4 hyperbilirubinemia is due to the indirect (unconjugated) component only, and hemolysis as the etiology has been ruled out as per institutional guidelines (eg, review of peripheral blood smear and haptoglobin determination), then ψ pamiparib by 1 dose level and continue treatment at the discretion of the investigator in discussion with the medical monitor			
Aspartate aminotransferase (AS	oT) and/or alanine aminotransferase (ALT)			
Grade 3 (>5 and ≤20 × ULN)	 Hold pamiparib until AST and/or ALT resolved to ≤5 × ULN or baseline If ≤5 × ULN within 14 days, then ↓ pamiparib by 1 dose level If second episode, permanently discontinue pamiparib If persistent for >14 days, permanently discontinue pamiparib 			
Grade 4 (>20 × ULN)	Permanently discontinue pamiparib			

Toxicity	Recommended Dose Modification ^a
Pancreatic	
Pancreatitis	
Grade 3 or 4	Permanently discontinue pamiparib
Cardiac	
Cardiac - Prolonged QTc interv	al
QTcF >500 msec A change in QTc interval >60 msec from baseline or pre-dose value of whichever is the highest Cardiac - General	 Obtain triplicate ECGs (2 to 3 minutes apart) ~1 hour after initial ECG If mean QTcF >500 msec, or a change in QTc interval >60 msec from baseline, hold pamiparib until evaluation of ECGs by cardiologist Cardiology evaluation as soon as practical but within 7 days of initial abnormal ECG If mean QTcF >500 msec, or a change in QTc interval >60 msec from baseline confirmed by cardiologist, permanently discontinue pamiparib
Grade 3	Hold pamiparib until resolved to Grade ≤ 1 or baseline and Ψ pamiparib by 1 dose level
Grade 4	Permanently discontinue pamiparib
Other AEs	
Grade 3	Hold pamiparib until resolved to Grade ≤ 1 or baseline and ψ pamiparib by 1 dose level No dose reduction required for asymptomatic laboratory abnormalities
Grade 4 (>20 × ULN)	Permanently discontinue pamiparib

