Abbreviations: AE, adverse event; ALT, alanine aminotransferase; ANC, absolute neutrophil count; AST, aspartate aminotransferase; CKD-EPI EQ: Chronic Kidney Disease Epidemiology Collaboration Equation; ECG, electrocardiogram; Hgb, hemoglobin; PLT, platelet (count); QTc, QT interval corrected for heart rate; QTcF, QT interval corrected for heart rate using Fridericia's formula; ULN, upper limit of normal.

For Phase 2 portion, the dose level of pamiparib is 60 mg BID (level 1), 40mg BID (level -1) and 20mg BID (level -2). Reescalation using intermediate doses may be possible providing tolerability is good, please contact sponsor medical monitor for discussion.

In the event of a DLT (see Table 4), treatment will be stopped and supportive therapy administered as required. If the toxicity resolves or subsides to Grade 0, Grade 1 or Grade 2 (Grade 2 is only applicable to neutropenia) within 14 days and interruption or delay of treatment for no more than 21 days of the onset of the DLT and the patient is showing clinical benefit in the investigator's opinion, resumption of treatment after resolution of a DLT will be at the next lower dose level tested

(or 50% lower if the DLT occurs with the first dose level). If the toxicity does not resolve to Grade 0, Grade 1 or Grade 2 (Grade 2 is only applicable to neutropenia) within 14 days of onset, the patient must be withdrawn from the study. Any exception to this must be agreed upon by the investigator and the medical monitor.

For management and follow-up of toxicity also refer to Section 4.1.3.

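### Table 9's first-anemia step pairs a one-level reduction with a fixed 40 mg BID, and the two agree only for a patient on 60 mg BID

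*Protocol*

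**What the plan says.** All the relevant text is in Protocol Section 5.2.1, Table 9 and its notes.

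- **First anemia step.** The trigger is "First occurrence of Hgb < 9.0 g/dL". Pamiparib is held and the patient treated until hemoglobin reaches 9 g/dL. Then comes a down-arrow followed by "pamiparib by 1 dose level to 40 mg BID".
- **Later anemia steps.** In the 8 to <9 g/dL and Grade 3 rows the condition is "Subsequent occurrence following dose reduction for anemia". One of three alternatives there is a down-arrow with "pamiparib by 1 additional dose level to 20 mg BID". In the Grade 4 row the same reduction is the only instruction for a second occurrence.
- **Other toxicities.** These rows use a relative step with no dose named. For febrile neutropenia it is "Hold pamiparib until resolved and ↓ pamiparib by 1 dose level". Neutropenia, thrombocytopenia, renal, bilirubin, AST/ALT, cardiac and other AEs have similar steps.
- **Notes in the anemia block.** One note allows a one-level reduction to be considered for a hemoglobin fall of more than 2 g/dL. Another makes a dose increase depend on medical monitor approval and on hemoglobin staying above 9 g/dL for at least 3 months.
- **Ladder and cap.** For Phase 2, "the dose level of pamiparib is 60 mg BID (level 1), 40mg BID (level -1) and 20mg BID (level -2"). Also, "Each patient is only allowed up to 2 dose reductions".
- **Other AEs.** The row that requires permanent discontinuation is labelled "Grade 4 (>20 × ULN"). The AST/ALT Grade 4 row uses the same cut-off. The Other AEs Grade 3 row has no ULN limit.

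**The concern.** A relative step and a fixed dose in one instruction are harmless only if every patient who meets the trigger is on the same dose. Here the trigger is a first hemoglobin value, whatever the current dose, and seven other groups of toxicity can lower the dose first. A site treating such a patient has to choose which half of the sentence to follow, and two sites could follow the same row to different restart doses.

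Anemia is the toxicity for which this matters most. The protocol's summary of changes lists a revised Phase 2 anemia algorithm, and SAP Section 6.7 says version 5.0 was mainly meant to give a more proactive dose-modification algorithm and closer hematology monitoring.

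The ULN label is a smaller, separate matter. It affects whether the row for Grade 4 events not listed elsewhere reaches the events it seems meant for.

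**Working it through.** No sample-size arithmetic applies. The check walks down the protocol's dose ladder.

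**Inputs (all Section 5.2.1)**
- Ladder: 60 → 40 → 20 mg BID, nothing lower.
- First anemia step: one level down, named dose N = 40 mg BID.
- Later anemia option: one additional level down, named dose N = 20 mg BID.
- Cap: 2 reductions per patient, not limited by cause.

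**Rule.** Let L(d) be the next level below the current dose d, so L(60) = 40, L(40) = 20, and L(20) does not exist. The instruction is consistent only if L(d) = N. The change implied by the named dose is N − d.

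**First step (N = 40)**

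| Current dose | Reductions used | One level down | Named dose | N − d | Agree? |
|---|---|---|---|---|---|
| 60 mg BID | 0 | 40 | 40 | −20 | yes |
| 40 mg BID | 1 | 20 | 40 | 0 | no |
| 20 mg BID | 2 | none | 40 | +20 | no |

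The protocol's own figure of 40 mg BID is reproduced from 60 mg BID and from no other level. From 40 mg BID, the relative half is a cut of 20/40 = 50% and the fixed half is no cut. From 20 mg BID, 2 − 2 = 0 reductions remain, no lower level exists, and the named dose is 40/20 = 2 times the current one. That contradicts the down-arrow in the same line and would bypass the separate conditions for an increase.

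**Later option (N = 20)**

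| Current dose | One level down | Named dose | Agree? |
|---|---|---|---|
| 40 mg BID | 20 | 20 | yes |
| 20 mg BID | none | 20 | no |

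This option is also keyed to an earlier reduction for anemia. A reduction for another toxicity does not meet that condition.

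**Can these states occur?** Yes. A patient reaches 40 mg BID before a first hemoglobin below 9.0 g/dL through one reduction in a non-anemia row, or under the note on a fall of more than 2 g/dL. Two such reductions lead to 20 mg BID. For the later option, one non-anemia reduction followed by one anemia reduction is enough to be at 20 mg BID. The reduction counts assume no re-escalation in between.

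**Other AEs, Grade 4.** Set beside the AST/ALT row, the cut-off is identical. A Grade 4 event with no upper limit of normal cannot exceed 20 times that limit, so read literally the row does not cover it.

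**The case against.** **A reader might infer that the table orders a dose increase during anemia.** It does not. The line carries a down-arrow, and at 20 mg BID a reduction sign stands next to a higher figure, so the step cannot be executed; it does not instruct sites to double the dose. Restart also follows recovery to at least 9 g/dL, although Table 9 still grades 9 to <10 g/dL as Grade 2. Increases are controlled by the medical monitor note and by the re-escalation sentence under the table.

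**Oversight reduces the practical risk.** The column header calls the modifications recommended, and Section 5.2 requires the investigator and the medical monitor to agree on a toxicity-related delay. This stands as mitigation. But that agreement concerns the delay, and none of this text says which half of the sentence governs the restart dose.

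**A reader might infer that many patients are affected.** Section 1.4.3 reports related anemia in 8 of 15 Phase 1 patients and decreased neutrophil count in 7 of 15. These are separate counts: the overlap could be anywhere from 8 + 7 − 15 = 0 to 7. For the Grade 3 counts, 5 and 2, it could be 0 to 2. Table 9 reduces for Grade 3 neutropenia only if it takes more than 7 days to resolve, and no Grade 4 or higher event was reported. The reduction must also come before the first hemoglobin below 9.0 g/dL. All Phase 2 patients start at 60 mg BID, where the row is consistent.

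**A reader might infer that the analyses are compromised.** SAP Section 6.5.2 counts reductions from study medication data, so the counts reflect recorded dosing. The summaries by most recent dose level and by amendment period (SAP Section 6.7) are ad hoc and descriptive. The wording does not bear on how the primary ORR test is specified.

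**The later anemia rows are only partly affected.** In the 8 to <9 g/dL and Grade 3 rows, two of the three alternatives name no fixed dose. The Grade 4 second-occurrence line has no such alternative.

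**The ULN label looks like a copied qualifier.** Probably so, but the row still needs correcting.

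**Conclusion.** The inconsistency is real and limited. The first anemia step is coherent at one of three dose levels, contradicts itself at 40 mg BID (20 versus 40 mg BID), and cannot be carried out at 20 mg BID. The later option to 20 mg BID cannot be carried out as a reduction by a patient already at 20 mg BID. Counting levels is not counting patients: the documents give no figure for how many would meet the first anemia step below 60 mg BID, and the number could be small.

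The conclusion rests on reading the trigger as applying at any current dose, since no text restricts it, and the cap as covering reductions for all causes, since none is singled out. It does not extend to an ordered dose increase, to a common problem, or to an effect on the primary analysis. The Other AEs Grade 4 label is a separate and minor defect. Both are worth correcting because they sit in dosing instructions that sites apply directly.

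**What to change.** The sponsor should reconcile the anemia steps in Table 9 with the dose-level footnote, the cap of two reductions and the dose-increase note, so that each possible current dose has one consistent instruction. This should include patients already reduced for another toxicity or under the hemoglobin-fall note. The sponsor should also reconcile the ULN qualifier in the Other AEs Grade 4 row with the events that row is meant to cover. Which dose or rule applies is the sponsor's decision, and none is proposed here.

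The cost is table wording in an amendment or a site clarification letter. It needs no extra visits, data or patients.

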5.3 Treatment Assignment

Each patient enrolled in this study will receive a unique patient number which will be assigned when the patient is enrolled in the study. Patient will be assigned in chronological order starting with the lowest number. Once a patient number have been assigned to a patient, it cannot be reassigned to any other patient.

If a patient is replaced in Phase 1 portion, the replacement patient will be assigned the next available patient number.

5.4 Packaging and Labelling

Pamiparib capsules will be provided in a child-resistant high-density polyethylene bottle with an induction seal and bottle label. The label will include at a minimum, drug name, dose strength, contents, sponsor, protocol number, lot number, directions for use, storage conditions, caution statements, retest or expiry date, and space to enter the patient number and name of investigator.

The contents of the label will be in accordance with all applicable local regulatory requirements.

5.5 Handling and Storage

The pamiparib will be dispatched to a study center only after receipt of the required documents in accordance with applicable regulatory requirements and the sponsor's procedures.

Investigational pamiparib product must be dispensed or administered according to procedures described herein. Only patient enrolled in the study may receive pamiparib, in accordance with all applicable regulatory requirements. Only authorized study center personnel may supply or administer pamiparib. Pamiparib must be stored in a secure area with access limited to the investigator and authorized study center personnel and under physical conditions that are consistent with investigational product-specific requirements. Pamiparib must be kept at 15-30°C and protected from light.

5.6 Product Accountability

the investigator is responsible for pamiparib accountability, reconciliation, and record maintenance. In accordance with all applicable regulatory requirements, the investigator or designated study center personnel must maintain pamiparib drug accountability records throughout the course of the study. This person(s) will document the amount of pamiparib received from the sponsor, the amount supplied and/or administered to and returned by patients, if applicable.

After completion of the study, all unused pamiparib will be inventoried and packaged for return shipment by the hospital unit pharmacist. The inventoried supplies will be returned to the sponsor or destroyed on site, after receiving written sponsor approval.

5.7 Assessment of Treatment Compliance

On all visits to the study center, patients will be questioned in regard to compliance with study instructions.

5.8 Treatment of Pamiparib Overdose

Overdose is defined as: the patient has taken (accidentally or intentionally) a dose exceeding 120 mg BID or higher. Patients with a suspected overdose should be managed with appropriate supportive therapy as determined by the investigator in consultation with the medical monitor. Any adverse effects occurring as a result of an overdose should be reported to the medical monitor as well as being included in standard AE reporting.

5.9 Occupational Safety

Pamiparib is not expected to pose significant occupational safety risk to the study center personnel under normal conditions of use and administration. A material safety data sheet describing occupational hazards and recommended handling precautions will be provided to the investigator, where this is required by local laws, or is available upon request from the sponsor.

6 CONCOMITANT MEDICATIONS AND NON-DRUG THERAPIES

6.1 **Permitted Medications**

All treatments that the investigator considers necessary for a patient's welfare may be administered at the discretion of the investigator in keeping with the local standards of medical care. All concomitant medications taken during the study will be recorded on the eCRF including all prescription, over-the-counter (OTC) drugs, herbal supplements, and intravenous (IV) medications and fluids. If changes occur during the study period, documentation of drug dosage, frequency, route, and date will also be included on the eCRF.

All concomitant medications received within 30 days before the first dose of study medication and 30 days after the last dose of study medication should be recorded.

The eCRF entry must include the dose, regimen, route, indication, and start and stop dates of use of the prior and concomitant medication.

6.2 **Prohibited Medications**

Patients are not allowed to receive other anti-cancer therapy, including surgery, radiation therapy, immunotherapy, investigational agents, cytotoxic, biologic or hormone therapy, anti-cancer Chinese medicine or anti-cancer herbal remedies. Hormone replacement therapy is allowed. Bisphosphonate and denosumab use is permitted if the patient has already been receiving it at a stable dose for >28 days prior to Day 1.

The primary metabolic pathway for pamiparib involves the CYP3A isoform. Co-administration of strong/moderate inhibitors of CYP3A or strong CYP3A inducers with pamiparib is not permitted (FDA Drug Development and Drug Interactions: Table of Substrates, Inhibitors and Inducers). Please refer to the drugs/substances listed in Appendix 8 and to http://medicine.iupui.edu/clinpharm/ddis/main-table/ for a more complete list of medications that are not permitted.

Grapefruit juice is not allowed at any time during the study. No other dietary restrictions will apply.

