 - Removed "The data alert letter will automatically be submitted to sponsor or designee immediately after investigator signature"
 - Removed the content specifying the transmission rules of paper SAE forms under the situation when EDC is non-operational.
- Appendix 2 (Clinical Laboratory Assessments),
 - Updated "Blood urea nitrogen" to "Blood urea nitrogen or urea" in Clinical Chemistry
 - Removed "and a random urine sample for total protein and creatinine to determine a protein to creatinine ratio" from the footnote
- Appendix 8 (Prohibited Medications), updated the food products among moderate CYP3A inhibitors from "grapefruit juice (citrus paradisi fruit juice)" to "grapefruit and juice (*Citrus paradisi*), Seville orange and juice (*Citrus aurantium*)"

SYNOPSIS

Name of Sponso	r/Company: BeiGene (Beijing)	Co., Ltd
Name of Finish	d Product: Pamiparib (BGB-2	90) Capsules
Name of Active	ngredient: Pamiparib (BGB-2	90)
Title of Study:	BGB-290 in Chinese Subjects v	hase I/II Study to Evaluate Efficacy and Safety of vith Advanced Ovarian Cancer, Fallopian Cancer, and dvanced Triple Negative Breast Cancer
Protocol No:	BGB-290-102	
Study Centers:	Phase 1: in 2 study centers Phase 2: in 25 to 35 study center	rs
Study Duration		Phase: 1/2
repeated treatme pamiparib [also] disease progress for further treatm	ening (up to 21 days), treatment cycle of t cycles of 21 days, safety follow-up (2 nown as BGB-290]). Patients will cont on, intolerable toxicity, withdrawal of c ent at the discretion of the investigators	50 ± 5 days after the last dose of inue treatment until confirmed onsent, or deemed unacceptable s, whichever occurs first.
follow-up $(30 \pm $	ening (up to 21 days), repeated treatmed days after the last dose of pamiparib). isease progression, intolerable toxicity, nvestigators.	Patients will continue treatment
Objectives:	Phase 1	
	Primary:	
	• To evaluate the safety and Chinese patients	olerability of pamiparib for advanced cancer in
	• To determine the recomme	nded Phase 2 dose (RP2D) of pamiparib
	Secondary:	
	• To characterize the pharma	cokinetics (PK) of pamiparib in Chinese patients
	triple negative breast cance	i-tumor activity of pamiparib in Chinese patients with r (TNBC) or high-grade epithelial, non-mucinous allopian cancer, or primary peritoneal cancer)
	• To evaluate the relationship	between pamiparib PK and clinical endpoints
	Exploratory:	
	•	
	Phase 2	
	Primary:	

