- 11. Use ≤ 10 days (or ≤ 5 half-lives, whichever is shorter), prior to Day 1, or anticipated need for food or drugs known to be strong or moderate CYP3A inhibitors or strong CYP3A inducers (Appendix 8)
- 12. Pregnancy or nursing:
 - Females of childbearing potential require a negative urine or serum pregnancy test ≤ 7 days

before Day 1

- 13. Significant intercurrent illness that may result in the patient's death prior to death from HGOC, or TNBC (only for Phase 1 portion)
- 14. Known history of intolerance to the excipient of the pamiparib capsule
- 15. Previous complete gastric resection, chronic diarrhea, active inflammatory gastrointestinal disease, or any other disease-causing malabsorption syndrome
 - Gastroesophageal reflux disease under treatment with proton pump inhibitors is allowed
- 16. Active bleeding disorder, including gastrointestinal bleeding, as evidenced by hematemesis, significant hemoptysis, or melena ≤ 6 months before Day 1
- 17. Any illness that investigator thinks makes the patient unsuitable for entry into the study
- 18. Unsolved acute effects of prior therapy of \geq Grade 2
 - Except for AEs not considered a likely safety risk (eg, alopecia, neuropathy, and specific laboratory abnormalities)

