4.2.3.1 Patient Restrictions

The following restrictions may affect patient participation in this study:

- The investigator must be informed as soon as possible about any medications taken from the time of screening until the patient is discharged from the study
- In Phase 1 portion, patients will be required to fast for 2 hours before and 1 hour after pamiparib administration on all days throughout the study, water will be allowed freely. Grapefruit juice is not allowed throughout the study. No other dietary restrictions will apply
- In Phase 2 portion, patients will be instructed to swallow the capsules whole, in rapid succession, with water. Pamiparib can be administered with or without food based on the pamiparib food effect evaluation result

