5.2 Dosage and Administration

Phase 1 Portion

The pamiparib will be taken once on Day 1 of Cycle 1 (morning only), followed by a 1-day treatment-free period (Day 2). Regular daily administration of pamiparib will commence on the morning of Day 3 of Cycle 1, as a 21-day period of repeated drug administration (Days 3 to 23). During subsequent cycles, the patients will take pamiparib BID from Day 1 to Day 21 (with no treatment-free or rest period).

Patients will be required to fast for at least 2 hours before and 1 hour after each administration of pamiparib throughout the study.

Phase 2 Portion

The patients will take pamiparib at 60 mg BID daily from Day 1 of Cycle 1 (with no treatment-free or rest period). Pamiparib capsules will be administered PO BID, once in the morning and once in the evening. The time difference between two consecutive doses will be approximately 12 hours with a window of ± 4 hours. Patients will be instructed to swallow the capsules whole, in rapid succession, with water. Pamiparib can be administered with or without food. However, to reduce gastrointestinal irritation that parmiparib may cause, patients are encouraged to take parmiparib with food.

A dose of pamiparib should be skipped if it is not taken within the upper range of the scheduled time, ie, within 16 hours. An extra dose of pamiparib should not be taken to make up for a missed dose. If vomiting occurs during the course of treatment, no re-dosing of the patient is allowed before the next scheduled dose.

On days with PK assessments, the morning dose of pamiparib should be administered in the clinic in accordance with the schedule for the PK samples.

The toxicity-related treatment delay must be agreed upon by the investigator and the sponsor Medical Monitor.

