APPENDIX 8: PROHIBITED MEDICATIONS

Strong and Moderate CYP3A Inhibitors and Strong CYP3A Inducers

Strong CYP3A Inhibitors
Antibiotics: clarithromycin, telithromycin, troleandomycin
Antifungals: itraconazole, ketoconazole, posaconazole, voriconazole
Antivirals: boceprevir, telaprevir
Other: cobicistat, conivaptan, elvitegravir, mibefradil, nefazodone,
Protease Inhibitors: indinavir, lopinavir, nelfinavir, ritonavir, saquinavir, tipranavir
Strong CYP3A Inducers
Avasimibe, carbamazepine, mitotane, phenobarbital, phenytoin, rifabutin, rifampin (rifampicin), St.
John's wort (hypericum perforatum)
Moderate CYP3A Inhibitors
Antibiotics: ciprofloxacin, erythromycin
Antifungals: fluconazole
Protease inhibitors: amprenavir, atazanavir, darunavir, fosamprenavir
Calcium channel blockers: diltiazem, verapamil
Tyrosine kinase inhibitors (anti-cancer): imatinib
Food products: grapefruit and juice (Citrus paradisi), Seville orange and juice (Citrus aurantium)
Herbal medications: Schisandra sphenanthera
Others: aprepitant, casopitant, cimetidine, cyclosporine, dronedarone, tofisopam

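### Protocol section 6.2 rules out every dietary restriction except grapefruit juice, yet the same section and Appendix 8 prohibit whole grapefruit and Seville orange (fruit and juice)

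*Protocol*

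**What the plan says.** Section 6.2 (Prohibited Medications) identifies CYP3A as the main route by which pamiparib is metabolised and then states: "Co-administration of strong/moderate inhibitors of CYP3A or strong CYP3A inducers with pamiparib is not permitted". For the items covered it tells sites: "Please refer to the drugs/substances listed in Appendix 8". The next paragraph, standing alone, reads: "Grapefruit juice is not allowed at any time during the study. No other dietary restrictions will apply".

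Appendix 8 is headed as a list of prohibited medications. Under moderate CYP3A inhibitors it includes the line "Food products: grapefruit and juice (Citrus paradisi), Seville orange and juice (Citrus aurantium".

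Three other places bear on diet:

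- **Section 4.2.2, exclusion criterion 11** excludes patients with recent use of, or "anticipated need for food or drugs known to be strong or moderate CYP3A inhibitors or strong CYP3A inducers (Appendix 8".
- **Section 4.2.3.1, Phase 1 bullet** says: "Grapefruit juice is not allowed throughout the study. No other dietary restrictions will apply". The Phase 2 bullet covers how to swallow the capsules and allows dosing with or without food. It names no food to avoid.
- **Section 5.2, Phase 1 portion** adds a fasting rule: "Patients will be required to fast for at least 2 hours before and 1 hour after each administration of pamiparib throughout the study".

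**The concern.** The dietary sentence in section 6.2 does more than omit some foods. It says that nothing beyond grapefruit juice is restricted. That conflicts with the paragraph above it and with the appendix that paragraph relies on, and no rule says which statement prevails.

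At stake is what enrolled patients are told to avoid. The protocol treats moderate CYP3A inhibition as reason enough to prohibit a co-administered substance. A site that counsels from the sentence dealing specifically with diet would allow foods the protocol itself places in that class. The synopsis plans 25 to 35 Phase 2 centers, so counselling could also differ from site to site.

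**Working it through.** No formula applies, and the plan gives no figure to reproduce. The check sets the current texts side by side.

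**Step 1: foods prohibited by way of Appendix 8.** Section 6.2 bars moderate CYP3A inhibitors and refers to Appendix 8. The reference covers substances as well as drugs. The appendix food line names 2 fruits, each as fruit and as juice: 2 × 2 = 4 items.

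**Step 2: foods barred by the section 6.2 dietary sentence.** It names 1 item, grapefruit juice, and denies any further restriction.

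**Step 3: compare.**

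| Food | Appendix 8 | Section 6.2 dietary sentence, read literally |
|---|---|---|
| Grapefruit juice | prohibited | barred |
| Whole grapefruit | prohibited | allowed |
| Seville orange | prohibited | allowed |
| Seville orange juice | prohibited | allowed |

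The difference is 4 − 1 = 3 items. One fruit (Seville orange) is missing altogether, and the other is covered only as juice.

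**Step 4: is food meant to fall under the CYP3A rule?** Yes. Exclusion criterion 11 names food explicitly and cites the same appendix. It is applied at entry, however, and does not tell an enrolled patient what to avoid.

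**Step 5: does another on-study instruction settle it for Phase 2?** No. The grapefruit wording in section 4.2.3.1 sits in the Phase 1 bullet only. The section 6.2 sentence is therefore the only sentence about foods to avoid on study that reaches Phase 2 patients.

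**Step 6: does the finding depend on the amendment log?** No. It stands on section 6.2 and Appendix 8 as they now read. As background, the version 5.0 log records that the sponsor "updated the food products among moderate CYP3A inhibitors from" grapefruit juice alone to the present line. The section 6.2 sentence still matches that narrower scope, which suggests it was not updated with the appendix.

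**The case against.** The strongest reply is that the prohibition is already in section 6.2, one paragraph above, so the closing sentence can be taken to mean that nothing applies beyond what has already been stated. Section 4.2.3.1 lends this some support: there the same wording follows the Phase 1 fasting rule and plainly does not cancel it. Exclusion criterion 11 also looks ahead to anticipated need, so the intent to control food reaches past Day 1. On this view the sentence is imprecise and gives no permission.

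That reading is possible but strained for section 6.2. The two dietary sentences form their own paragraph, name one food, and then deny any other restriction. They are also what a site would naturally consult on diet.

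Some limits do stand:

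- Harm requires a site to follow the sentence and overlook the paragraph above it, the appendix and criterion 11. The consent pages are not in the review copy, so what patients are actually told cannot be checked.
- The Phase 1 edit has little practical effect. SAP section 1 says most Phase 1 patients had ended the study before protocol version 2.0 was released.
- A short cross-reference to Appendix 8 would remove the conflict. A clause on other CYP3A-active foods goes further than the four listed items, but it only carries the scope of criterion 11 into the treatment period.

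**Conclusion.** The concern holds: the section 6.2 dietary sentence is wrong as written. Taken literally it allows 3 of the 4 foods that Appendix 8 prohibits. This rests on the current wording alone and on reading the denial of further restrictions at face value.

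It is a minor point of safety and conduct. Without an interaction size or intake data in the documents, no change in exposure and no patient count can be given, and none is claimed. The ORR hypothesis test, the sample size and the power do not depend on it.

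**What to change.** Replace the two dietary sentences in section 6.2 with wording such as:

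*Throughout the study, patients must not consume grapefruit or Seville orange, the juice of either, or any other food that is a strong or moderate inhibitor or a strong inducer of CYP3A (see Appendix 8). Apart from the Phase 1 fasting rule in sections 4.2.3.1 and 5.2, diet is otherwise unrestricted.*

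The fasting exception is needed because section 6.2 covers both phases, and an unqualified statement that nothing else is restricted would clash with the Phase 1 rule (2 hours before to 1 hour after each dose). Make the matching change to the Phase 1 bullet of section 4.2.3.1 for consistency.

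The cost is one rewritten passage and one matching edit at the next amendment, with IEC/IRB review where applicable under section 11.2. There is no new data collection and no statistical cost.
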